5.3 Randomization and Blinding

Subjects will be randomized in a 2:1 ratio to receive an oral tablet of either ADX-629 300 mg BID or placebo BID for up to 28 days. Subjects, Investigators, and clinical trial personnel (including the Sponsor/designee) involved in the administration and assessment of the study drug will be blinded to the subject treatment assignments throughout the clinical trial.

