3 CLINICAL TRIAL DESCRIPTION

3.1 Summary of Clinical Trial Design

ADX-629-COVID-19-001 is a Phase 2a, randomized, double-blind, placebo-controlled, clinical trial to evaluate the safety, tolerability, efficacy, and PD of ADX-629, administered orally, in adult subjects with COVID-19 of moderate severity prior to the requirement for mechanical ventilation. Approximately 30 subjects will be randomized in a 2:1 ratio (ADX-629 to placebo) to receive either ADX-629 300 mg BID or placebo BID for up to 28 days.

The reason for hospital admission (for hospitalized subjects), the standard of care (see Section 5.6.3) followed for each subject and site, and whether any care decisions were based on resource limitations will be clearly documented for all subjects.

Treatment will begin on Day 1 following randomization. In addition to ADX-629 or placebo, all subjects will receive standard of care treatment for COVID-19. Treatment may commence whether a subject is hospitalized or is treated as an outpatient at Screening. During the Treatment Period (Days 1 to 28/End of Treatment [EOT]), all subjects will receive study drug (either ADX-629 or placebo) BID. The study drug will continue to be taken on an outpatient basis if a subject is discharged from the hospital prior to Day 28 for hospitalized subjects. If a subject is placed on mechanical ventilation and/or is otherwise unable to ingest an oral tablet, dosing will be stopped. However, the subject will continue to be monitored for efficacy and safety. Dosing of the study drug may resume once the subject is able to safely ingest an oral tablet.

All subjects will also have an assessment using the NIAID ordinal scale score (see Appendix C) daily on Days 1 to 28/EOT. The NIAID score will be evaluated directly for inpatient subjects and assessed via a subject diary for outpatient subjects through Day 28.

After treatment is completed, subjects will undergo a follow-up visit on Day 35 (± 3 days) and a telephone follow-up on Day 60 (± 3 days). The purpose of the telephone follow-up is to assess survival status and evaluate for COVID-19 relapse. A telephone follow-up visit may be performed in lieu of the Day 35 follow-up visit if the subject is unable to attend in person.

The clinical trial will be conducted at approximately 3 sites in the United States.

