4.2 Exclusion Criteria

Subjects meeting any of the following criteria will be excluded from the clinical trial:

1. Has an NIAID ordinal scale score <5 (see Appendix C);
2. Is on high-flow oxygen or any form of noninvasive ventilation, excluding continuous positive airway pressure (CPAP) alone for sleep disorders (e.g., obstructive sleep apnea);
3. [REDACTED]
4. [REDACTED]
5. Has a history of chronic obstructive pulmonary disease or bronchial asthma requiring continuous treatment and/or intermittent or continuous oxygen within the last 90 days prior to Screening or has significant lung infiltrates on chest X-ray (e.g., involving >50% of lung fields) at Screening as determined by the Investigator;
Note: Intermittent use of a β 2-agonist inhaler is allowed.
6. Has had any form of mechanical ventilation (invasive or noninvasive, excluding CPAP alone) for structural lung disease, neuromuscular disease, or another condition requiring chronic mechanical ventilation;
7. [REDACTED]
8. [REDACTED]
9. [REDACTED]
10. Has a history of human immunodeficiency virus (HIV), hepatitis B, or hepatitis C infection or has a positive HIV antibody, hepatitis B surface antigen (HBsAg), or hepatitis C virus (HCV) antibody result at Screening;
11. Has a current or previous severe allergy and/or hypersensitivity to ADX-629 or its excipients;
12. Is pregnant or lactating or plans to become pregnant during the clinical trial;
Note: A serum human chorionic gonadotropin (hCG) test will be performed in all WCBP at Screening.
13. Is male and has known hypogonadism and hypospermia;

14. Is currently on another systemic immunomodulatory therapy (e.g., corticosteroid, calcineurin inhibitor, hydroxychloroquine, anti-cytokine therapy, Janus kinase inhibitor) except for daily prednisone (or corticosteroid equivalent) ≤ 10 mg/day or inhaled or nasal corticosteroids;

Note: Dexamethasone 6 mg daily or equivalent is permitted after randomization at the Investigator's discretion for progression to severe or critical COVID-19 requiring invasive ventilation or oxygen therapy for hypoxemia.

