### 3.3.4 Demographic and Baseline Characteristics

The following demographic and baseline characteristics will be summarized:

- Age (years)
- Sex
- Race
- Ethnicity
- Inpatient (yes/no)
- SARS-CoV-2 test result (positive/negative)
- COVID-19 severity categorization
- Height (cm)
- Weight (kg)
- Body mass index (BMI) (kg/m^2)
- SARS-CoV-2 Variant (if available)

Demographic and baseline characteristics will be summarized with descriptive statistics or counts and percentages of subjects as appropriate by treatment and in total for all randomized subjects and each defined analysis population.

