## 3.4 Efficacy Assessment

Efficacy data (i.e., secondary endpoints) will be analyzed by randomized treatment based on the ITT Population. The key efficacy endpoint will also be analyzed based on the PP Population. The trial is exploratory and not formally powered. All assessments will be deemed exploratory.

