### 3.4.2 Other Efficacy Endpoints

Additional efficacy endpoints include the following:

- Proportion of subjects alive and not mechanically ventilated over Day 1 through Day 28;
- Time to recovery (for hospitalized subjects at Screening), defined as the first day on which the subject has an NIAID score of 6 or larger;
- Time to recovery (for non-hospitalized subjects at Screening), defined as the second consecutive day on which the subject has an improvement in the NIAID ordinal scale by 1 point;
- Proportion of subjects alive and not in the intensive care unit over Day 1 through Day 28;
- Proportion of subjects alive and not in the hospital over Day 1 through Day 28;

- Proportion of subjects alive and not on supplemental oxygen over Day 1 through Day 28;
- Mortality; and
- Time to hospital discharge (for hospitalized subjects), defined as time from first hospital admission to first hospital discharge in the 28 day study period.

The proportions will be presented by treatment group (ADX-629 or placebo). The difference between treatment groups will be analyzed by a Generalized Estimating Equation (GEE) model similar to the MMRM model for the key efficacy endpoint if applicable. If the GEE model does not converge, then the Fisher's exact test will be used.

Time to recovery (censored at Day 28) from randomization and time to hospital discharge will be addressed by Kaplan-Meier analysis, including a comparison between the treatment groups by a log-rank test if applicable.

The mortality rate, calculated as the number of subjects who died by Day 28 divided by the number of subjects randomized, will be summarized by treatment group. The difference between treatment groups will be analyzed by Fisher's exact test if applicable.

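### The hospital-status proportion pools inpatients and outpatients with no stratification or stated adjustment for entry setting, and its Day 1 to 28 window is undefined

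*Protocol*

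**What the plan says.** - **Allocation.** Protocol 5.3: "Subjects will be randomized in a 2:1 ratio to receive an oral tablet of either ADX-629 300 mg BID or placebo BID for up to" (…). SAP 2.2.2 repeats the sentence. Neither names a stratification factor or a block size.
- **Who enters.** Protocol 3.1: "Treatment may commence whether a subject is hospitalized or is treated as an outpatient at Screening". Exclusion criterion 1 (Protocol 4.2) removes NIAID scores below 5, so by Appendix C entry scores are 5 or 6 (hospitalized) or 7 or 8 (not hospitalized). No quota or expected mix is visible, though some eligibility and sample-size text is blacked out.
- **Endpoint.** SAP 3.4.2 lists "Proportion of subjects alive and not in the hospital over Day 1 through Day 28", with no restriction by setting. SAP 3.4: "Efficacy data (i.e., secondary endpoints) will be analyzed by randomized treatment based on the ITT Population".
- **Analysis.** SAP 3.4.2 compares the proportions with a GEE modelled on the MMRM of the key efficacy endpoint, and uses Fisher's exact test if the GEE fails to converge. SAP 3.4.1 describes no MMRM, only descriptive statistics, so the GEE terms are not stated.
- **Setting as data.** SAP 3.3.4 lists inpatient yes/no among the baseline characteristics to be summarized. No analysis is said to use it.
- **Endpoints already separated.** Time to recovery has one definition for subjects hospitalized at Screening and another for the rest. Time to discharge covers hospitalized subjects only.

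**The concern.** On Day 1, whether a subject is in hospital reflects where he or she entered the trial and not what the drug has done. An endpoint whose window opens on Day 1 therefore carries entry setting into the result. With unstratified allocation to arms of about 20 and 10, the inpatient share can differ noticeably between arms by chance, and an unadjusted comparison shows part or all of that gap as a treatment difference.

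At stake is how readable one secondary estimate will be. The recovery and discharge endpoints show that the plan already treats entry setting as important. This proportion lacks the same separation, and the variable needed to supply it is already collected.

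**Working it through.** The plan states no power, alpha or effect size, so there is no figure of its own to reproduce.

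**Inputs from the documents.** About 30 subjects at 2:1 (Protocol 3.1) gives 20 and 10.

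**Assumptions (not in the documents).** K inpatients among 30, with K from 5 to 20 in step 1. Inpatient share f from 30% to 70% in step 2. A proportion h of 5% to 10% of outpatients in hospital. Exponential discharge with a median stay m of 3 to 14 days. No drug effect.

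**Step 1: chance imbalance.** Let X be the number of inpatients on placebo, hypergeometric (30, K, 10). The arm difference in inpatient share is D = (K − X)/20 − X/10 = K/20 − 0.15X, so

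SD(D) = 0.15 × √[10 × (K/30) × (1 − K/30) × 20/29].

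For K = 10 this is 0.15 × √1.533 = 0.15 × 1.238 = 0.186.

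| K | SD of D (points) | P(\|D\| ≥ 30 points) |
|---|---|---|
| 5 | 14.7 | 3.1% |
| 10 | 18.6 | 10.1% |
| 15 | 19.7 | 24.5% |
| 20 | 18.6 | 10.1% |

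D moves in steps of 15 points, so tail probabilities jump. At K = 15, strictly more than 30 points has probability 5.0%.

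**Step 2: how much reaches the endpoint.** An imbalance D moves the arm difference by D × (p_out − p_in), where p is the success probability in each setting. The share of endpoint variance explained by setting is f(1 − f)(p_out − p_in)² / [p(1 − p)].

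- *Every day from Day 1.* p_in = 0. With h = 5%, p_out = 0.95. At f = 0.5, p = 0.475 and the share is 0.25 × 0.9025 / 0.2494 = 90%. Over f of 30–70% and h of 5–10% it is 73–93%. A 30-point imbalance moves the result by 27 to 29 points.
- *Each day separately* (f = 0.5, h = 5%). The fraction of inpatients still in hospital on day t is 0.5^((t − 1)/m). Over m of 3 to 14 days, setting explains 90% of variance on Day 1, 8–50% on Day 7, 0–28% on Day 14 and 0–9% on Day 28. A 30-point imbalance moves the 28-day average by about 4 to 15 points.
- *Day 28 status only.* At m = 14, 26.3% of inpatients remain, and a 30-point imbalance moves the result by 0.30 × (0.263 − 0.05) = 6.4 points. At m = 3 it moves it by 0.30 × (0.002 − 0.05) = −1.4 points.

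**Step 3: false positives.** Take the worst case for the fallback: the every-day reading, no drug effect, no outpatient admitted. Successes are then exactly the outpatients. At K = 10, two-sided Fisher at 0.05 rejects when X = 0 or X ≥ 6, which has probability 0.0061 + 0.0388 = 4.5%. It is 4.5% at K = 20, 3.1% at K = 5 and 0.5% at K = 15. The error rate is held. A single unlucky split can still mislead: 7/20 versus 8/10 inpatients gives 13/20 versus 2/10 successes, p = 0.050.

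**Step 4: precision.** On the every-day reading (f = 0.5, h = 5%), the SE of the arm difference is √[0.2494 × (1/20 + 1/10)] = 0.193 unadjusted. Within setting it is √[(0.2494 − 0.2256) × 0.15] = 0.060. On a day when half the inpatients remain, it goes from 0.173 to 0.149. When 10% remain it stays at 0.102. Part of the large first gain arises because inpatients then contribute nothing, so adjustment alone does not repair the every-day reading.

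**The case against.** The strongest defence is that unstratified 2:1 allocation is an ordinary choice in a 30-subject Phase 2a trial. The primary objective is safety, and all efficacy assessments are labelled exploratory. This is one of eight additional secondary endpoints and not the key one. Inpatient status will be tabulated by arm, so an imbalance would be seen. All of this stands, and it limits the severity.

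A reader might also infer four stronger things that the documents do not support.

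- *That hospital-based endpoints in general are pooled.* Recovery is split by setting and discharge is restricted to hospitalized subjects. Chance still decides the arm ratio within each setting: with 10 inpatients, there is a 25% chance that two or fewer are on placebo. With 15 inpatients it is 2.5%. Stratifying would turn 8 versus 2 into about 7 versus 3, which is little help to a log-rank test.
- *That the Fisher fallback forces the every-day reading.* It needs one yes or no per subject. Status on Day 28 supplies that equally well.
- *That the GEE omits setting.* Its terms are unspecified, so omission is not established. A baseline NIAID term, if intended, would largely capture setting. Only the fallback is clearly unadjusted.
- *That the result is biased or false positives are inflated.* Randomisation makes the imbalance symmetric in expectation, and step 3 shows that the test allows for it.

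The defence does not answer the undefined window, the unstated model terms or the unadjusted fallback, given that the adjusting variable is already collected.

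**Conclusion.** The point holds as a matter of definition and precision. No stratification is stated, the hospital-status proportion pools both settings, and no adjustment for setting is specified. Entry setting largely determines the endpoint only if the window means every day from Day 1. On a daily reading that is true of the early days, and by Day 28 setting explains at most about 9% of the variance under the assumed stays. The documents do not say which reading applies.

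The chance difference in inpatient share has an SD of about 15 to 20 points. That figure rests on an assumed 5 to 20 inpatients among 30, and the effects in step 2 rest also on assumed lengths of stay and outpatient hospitalisation. Severity is minor to moderate.

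**What to change.** In SAP 3.4.2:

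1. Define the hospital-status endpoint so that inpatients can meet it, for example status on fixed days after Day 1 such as Day 14 and Day 28. Do this first, since adjustment cannot rescue a definition that inpatients fail automatically.
2. Write out the GEE terms and include inpatient yes/no.
3. Replace the plain Fisher fallback with an exact test stratified by inpatient yes/no, applied at a named day.
4. Show the endpoint by entry setting and arm.

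These changes take a few lines and use data already collected. SAP 1 has the plan finalized before database lock, so they remain possible after enrolment starts.

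If enrolment has not begun, also stratify the 2:1 randomisation by setting in Protocol 5.3 and SAP 2.2.2. That adds one binary stratum to the list, and the downside is a few incomplete blocks. If enrolment has begun, the SAP changes alone deal with most of the problem.

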5.4 Breaking the Blind

The Investigator is responsible for the medical care of subjects during the clinical trial. In an emergency, when knowledge of the subject's treatment assignment is essential for the clinical management or welfare of the subject, the Investigator can unblind the treatment assignment. It is encouraged that the Investigator contact the Medical Monitor (or designee) before proceeding with the unblinding process. Unblinding should only occur for the subject in question if it is critical for treatment decision making by the Investigator for the well-being of the subject.

Prior to unblinding the subject's treatment assignment, the Investigator should assess the relationship of an AE to study drug (yes or no). If unblinding is warranted, the Investigator must then follow the appropriate procedures to unblind an individual subject's treatment assignment.

Generally, the blind should only be broken for events that are considered to be serious, unexpected, and causally related to the clinical trial treatments, or as requested by local regulatory authorities.

If the clinical trial blind is broken, the Investigator must detail the date and reason for unblinding in the subject's records. The Investigator must also notify the Sponsor (and Institutional Review Board [IRB] if applicable), if this has not already been done, that the clinical trial blind has been broken. If the blind is broken due to an AE, the AE form must be completed and reported to the Sponsor (see Section 8.6).

5.5 Drug Supplies

5.5.1 Formulation and Packaging

Aldeyra Therapeutics, Inc. will supply sufficient quantities of study drug (ADX-629 and matched placebo) to allow for completion of the clinical trial. The lot numbers will be recorded in the final clinical trial report.

ADX-629 and the corresponding placebo will each be available as a tablet for oral administration. The study drug will be packaged in a kit with 2 bottles, each bottle containing thirty (30) 300 mg tablets. See the Pharmacy Manual for further details.

5.5.2 Study Drug Preparation and Dispensing

[REDACTED]

5.5.3 Study Drug Administration

[REDACTED]

Each subject will receive either ADX-629 300 mg BID or placebo BID for up to 28 days. If a subject is temporarily unable to tolerate dosing, a temporary dose interruption of up to 2 days may be permitted, after discussion with the Medical Monitor. No dose reductions will be permitted.

5.5.4 Treatment Compliance

The Investigator is responsible for maintaining specific subject records to document all study drug dispensed, administered, and returned.

5.5.5 Storage and Accountability

The pharmacist (or designee) will acknowledge receipt of all shipments of the study drug and maintain an inventory. The study drugs must be kept in a locked area with restricted access and stored and handled in accordance with the manufacturer's instructions. The pharmacist (or designee) will also keep accurate records of the quantities of the study drugs dispensed and used by each subject. The clinical research associate (CRA) will periodically check the supplies of study drugs held by the pharmacist to verify accountability of all study drugs used.

At the conclusion of the clinical trial, all unused study drugs will be returned to the Sponsor unless other arrangements have been approved by the Sponsor. The Sponsor will verify that a final report of drug accountability to the unit dose level is prepared and maintained in the Investigator clinical trial file.

[REDACTED]

5.6 Prior and Concomitant Medications and/or Procedures

5.6.1 Excluded Medications and/or Procedures

This figure is a 2D grayscale heatmap. It features a complex, multi-peaked structure in the center, characterized by several bright, localized peaks of varying intensities. The background is dark, and the overall shape is roughly rectangular but with irregular, jagged edges. The image is framed by a thick black border.

5.6.2 Documentation of Prior and Concomitant Medication Use

Prior medications used within the 7 days prior to randomization will be recorded. Prior medications must be recorded on the appropriate eCRF along with the reason for use, dates of administration, and dosages.

10. *Journal of the American Statistical Association*, 1990, 85, 1302-1313.

decided upon on an individual basis by the Investigator in consultation with the Medical Monitor.

Any medication taken by the subject during the clinical trial, from the time of informed consent, should be considered a concomitant medication. All concomitant medications through and including Day 60 must be recorded in the subject's eCRF along with the reason for use, dates of administration, and dosages. Concomitant medications given to treat any SAEs will be recorded in the eCRF through the end of the clinical trial.

5.6.3 Documentation of Standard of Care Medications and Procedures

The standard of care that was followed for each subject and site must be recorded throughout the treatment period, from Day 1 through Day 28, and at the follow-up visit (Day 35). If standard of care therapies or procedures are not able to be delivered due to resource limitations, this should

also be recorded. The specific resource limitation, including subject-related limitations (e.g., financial, social) and/or healthcare-related limitations (e.g., equipment shortage, clinician shortage) will be recorded on the appropriate eCRF.

Data regarding the clinical decision making that guides removal from mechanical ventilation, in relation to clinical deterioration, lack of clinical response, or other reasons will be recorded on the appropriate eCRF.

6 CLINICAL TRIAL PROCEDURES

The clinical trial procedures are described in Appendix A.

6.1 Informed Consent

A written (or electronic) ICF, or equivalent consent per FDA guidelines on COVID-19 clinical trials, must be obtained from the subject, or a legally authorized representative, prior to performing any protocol-specific procedure. See Section 11.3.

6.2 Screening Visit (Day -3 to 1)

The following procedures will be performed at Screening (Day -3 to 1):

- Obtain informed consent;
- Review inclusion and exclusion criteria;
- Obtain demographic information;
- Obtain medical/surgical history;
- Assess NIAID score (see Appendix C);
- Measure weight and height and calculate body mass index;
- Perform full physical examination;
- Measure vital signs;
- Perform PCR or another commercial or public health assay for SARS-CoV-2, and perform a confirmatory test for SARS-CoV-2 (if not done within 3 days [72 hours] of randomization), only if no documented, laboratory-confirmed SARS-CoV-2 infection test result is available;
- Perform serum hCG test (WCBP only);
- Perform FSH testing (naturally postmenopausal women only);
- Perform HIV, HBsAg, and HCV testing, only if status is unknown;
- Perform clinical laboratory assessments;
- Perform 12-lead electrocardiogram (ECG);

Note: ECG may be performed on Day 1, if not done at Screening, but it must be performed before the first dose of study drug is given.

- Perform chest X-ray;
- Record concomitant medications; and
- Record AEs.

6.3 Treatment Period – Days 1 Through 28/EOT

During the Treatment Period, all subjects will receive study drug (either ADX-629 or placebo) BID on Days 1 to 28/EOT. Treatment may commence whether a subject is hospitalized or is treated as an outpatient at Screening. The study drug will continue to be taken on an outpatient basis if a subject is discharged from the hospital prior to Day 28 for hospitalized subjects. The study drugs will each be administered orally BID, at the discretion of the Investigator, without food, defined as no food for at least 2 hours prior to dosing and at least 1 hour after dosing. Inpatient subjects will receive the study drug in the hospital. Outpatient subjects will take the study drug at home according to their usual schedule, including on Days 1, 7, 13, 22, and 28.

All subjects will also have an assessment using the NIAID ordinal scale score (see Appendix C) daily on Days 1 to 28/EOT. The NIAID score will be evaluated directly for inpatient subjects and assessed via a subject diary for outpatient subjects through Day 28. For outpatient subjects, the subject will receive instructions for subject diary completion on Day 1, while inpatient subjects will receive instructions on the day of discharge. Site personnel will monitor subject compliance between onsite study visits and contact subjects who are not compliant with diary completion. Subject compliance (for outpatient subjects only) for the subject diaries should be reviewed at the onsite visits at Days 7, 13, 22, and 28.

Inpatient subjects will have an assessment of standard of care (see Section 5.6.3) daily on Days 1 to 28/EOT (or until discharge). Outpatient subjects will have an assessment of standard of care (see Section 5.6.3) at each visit through Day 28.

In addition to study drug administration and NIAID score assessment, the procedures listed below will be performed on Days 1, 4, 7, 10, 13, 16, 19, 22, 25, and 28/EOT (inpatients). Subjects who commence treatment as outpatients or who are discharged from the hospital prior to Day 28 will undergo a telephone visit on Day 4 to assess safety and weekly onsite visits through Day 28 (on Days 7, 13, 22, and 28), which will include vital sign assessments, physical examinations, and local laboratory evaluations, as indicated below.

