6.3.1 Day 1 of Clinical Trial

The following procedures will be performed at Day 1:

- Review inclusion and exclusion criteria;
- Perform targeted physical examination;
- Measure vital signs;
- Perform clinical laboratory assessments;
- Perform 12-lead ECGs at 1 hour and 6 hours post-dose;

Note: If a 12-lead ECG was not performed at Screening, the subject should have a pre-dose ECG performed in addition to the post-dose ECGs.

- Obtain blood sample for PD analyses as follows: pre-dose (within 2 hours before the first dose of study drug) and post-dose (within 1 hour);

Note: The exact time (in minutes) of the blood sample(s) must be recorded in the eCRF.

- Record concomitant medications;

- Record AEs;
- Assess NIAID score;
- Record standard of care received;
- Perform randomization; and
- Administer study drug (to hospitalized subjects only).

Note: Outpatient subjects will take the study drug at home according to their usual schedule.

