6.3.3 Day 7 of Clinical Trial

The following procedures will be performed at Day 7 for all subjects as indicated:

- Perform targeted physical examination;
- Measure vital signs;
- Perform clinical laboratory assessments;

Note: Subjects who are outpatients may use a local laboratory.

- Perform 12-lead ECG (inpatients only);

- Obtain blood sample for PD analyses post-dose (within 1 hour);

Note: The exact time (in minutes) of the blood sample must be recorded in the eCRF.

Note: Subjects who are outpatients may use a local laboratory.

- Record concomitant medications;
- Assess NIAID score;
- Assess subject diary compliance (for outpatient subjects only);
- Record standard of care received;
- Record AEs; and
- Administer study drug (to hospitalized subjects only).

Note: Outpatient subjects will take the study drug at home according to their usual schedule.

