8.8 Vital Signs

Vital signs will include temperature, heart rate, blood pressure, respiratory rate, and oxygen saturation. Vital signs will be collected BID, both times prior to dosing with ADX-629. On Day 1, vital signs will also be collected at 2, 4, 6, and 8 hours post the morning dose.

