8.10 Electrocardiograms

Twelve-lead ECGs will be performed at Screening or Day 1 (pre-dose), on Day 1 at 1 hour and 6 hours post-dose, and on Day 7. Whenever ECGs and blood samples are specified to be collected at the same time, ECGs will be obtained before the blood samples. ECGs should be obtained in digital format when possible and archived.

Subjects should be in a supine position for at least 10 minutes prior to the ECG measurement. The ECG measurements will include heart rate, RR-interval, PR-interval, QT-interval, QRS-complex, and QTcF.

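### Outpatients are told to take the first dose at home, but the Day 1 PD sample and ECGs are timed from that dose; the Day 7 ECG and later PD samples need smaller clarifications

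*Protocol*

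**What the plan says.** Subjects may start treatment either in hospital or as outpatients (Protocol 6.3). For outpatients the rule is "Outpatient subjects will take the study drug at home according to their usual schedule, including on Days 1, 7, 13, 22, and 28". The Day 1 list in 6.3.1 repeats the home-dosing instruction in a note and confines site dosing: "Administer study drug (to hospitalized subjects only".

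The same list asks for blood for PD "pre-dose (within 2 hours before the first dose of study drug) and post-dose (within 1 hour", and for ECGs: "Perform 12-lead ECGs at 1 hour and 6 hours post-dose". Neither item is limited to inpatients. Protocol 8.8, repeated in SAP 3.6.3, adds: "On Day 1, vital signs will also be collected at 2, 4, 6, and 8 hours post the morning dose".

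For Day 7, Protocol 6.3.3 reads "Perform 12-lead ECG (inpatients only". Protocol 8.10 gives the post-dose ECG schedule as "on Day 1 at 1 hour and 6 hours post-dose, and on Day 7", with no restriction by setting, and SAP 3.6.5 does the same.

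PD samples within 1 hour after dosing are also due on Days 7, 13, 22 and 28. On those days the protocol adds "Subjects who are outpatients may use a local laboratory". That note does not accompany the Day 1 draw. SAP 3.5 summarizes PD at pre-dose and post-dose for each scheduled visit and gives no window rule.

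**The concern.** The Day 1 post-dose measurements are anchored to an event that, for outpatients, happens away from the site at a time the site does not control. A usual schedule also has no clear meaning for a first dose. If sites follow the text, an outpatient's post-dose PD sample and ECGs are either not taken or taken at some other interval. If the subject goes home and doses later, even the pre-dose PD sample may fall outside its 2-hour window.

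ECGs are a component of the primary safety endpoint (Protocol 7.1), and plasma RASP is a secondary objective (Protocol 2.2). SAP 3.6.5 summarizes ECG change to each scheduled post-dose time point, so a missing or mistimed Day 1 value enters those tables directly. The Day 7 wording is a smaller matter: two sites could apply different rules and each point to protocol text.

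**Working it through.** There is no stated figure to reproduce. The check is a comparison of sections and a count.

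**Step 1. Day 1 items against dosing location**

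| Day 1 item | Time after dose | Source | Limit by setting |
|---|---|---|---|
| Study drug given by site | 0 | Protocol 6.3.1 | hospitalized only |
| PD sample | within 1 h | Protocol 6.3.1 | none stated |
| ECG | 1 h | Protocol 6.3.1, 8.10 | none stated |
| ECG | 6 h | Protocol 6.3.1, 8.10 | none stated |
| Vital signs, 4 sets | 2, 4, 6, 8 h | Protocol 8.8, SAP 3.6.3 | none stated; context reads as inpatient |

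PD and ECG items with no practicable route for a home-dosing outpatient: 1 + 2 = 3. If the vital signs are also meant for outpatients: 3 + 4 = 7.

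**Step 2. Does the Day 1 list cover outpatients?** It includes the eligibility review and randomization, which every subject needs, and it carries a note addressed to outpatients. The lists for Days 10, 16, 19 and 25 are expressly confined to admitted subjects, and Day 4 has separate inpatient and outpatient lists. Day 7 marks its ECG item individually. In the Day 1 list only the dosing item is marked. As written, the list therefore covers outpatients.

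**Step 3. Scheduled post-dose ECGs per subject**

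- Inpatient: 2 (Day 1) + 1 (Day 7) = 3.
- Outpatient whose Day 1 ECGs are missed, under 6.3.3: 0 + 0 = 0.
- The same outpatient, under a literal reading of 8.10 and SAP 3.6.5: 0 + 1 = 1.
- Outpatient under the proposed fix: 1 (Day 1, 1 h) + 0 = 1, or 2 if the sponsor chooses to extend the Day 7 ECG.

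**Step 4. Later PD samples.** Post-dose PD days are 1, 7, 13, 22 and 28. All 5 are named as home-dosing days in 6.3. On the last 4 the sample can be within 1 hour of dosing only if the subject times the dose to the draw. The visible text requires the exact time of the sample but not of the preceding outpatient dose. From Day 7 this also applies to subjects who started in hospital and have been discharged.

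**Step 5. How many subjects.** About 30 are planned. The visible text gives no expected outpatient share, so the number affected on Day 1 lies between 0 and about 30.

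**The case against.** The strongest reply is that the decisive text may be out of sight. Section 6 refers to Appendix A for procedures, and the schedule itself is not shown. Section 5.5.2 is redacted, as is part of 5.5.3. A first-dose rule, an outpatient footnote or a dose-time field could be in any of them. This lowers confidence but does not remove the point. If the hidden text puts the first dose on site, 6.3 and 6.3.1 contradict it. If it exempts outpatients from the timed items, 6.3.1 and 8.10 do not say so. The visible wording needs alignment either way.

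The second reply is that 6.3 tags the procedure days, Day 1 among them, as inpatient days and names outpatient on-site visits only from Day 7. This carries real weight for the vital signs: 8.8 places the 2 to 8 hour sets beside twice-daily pre-dose measurements, which fit only a hospital stay. It carries less for the PD sample and ECGs, for the reasons in Step 2.

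Third, timing the dose to the draw on Days 7 to 28 is implied by the 1-hour requirement. That is fair, but it sits against an instruction to keep to the usual schedule, and one sentence would settle it.

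A reader might go further in four ways that the documents do not support.

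- That outpatients are owed a Day 7 ECG. Section 6.3.3 is the specific rule, and the outpatient visit content in 6.3 names no ECG. Sections 8.10 and SAP 3.6.5 are merely silent on setting.
- That this leaves a known cardiac risk unwatched. Protocol 1.1.2 reports no QTcF prolongation, no value above 500 ms and no change above 60 ms.
- That the setting behind a missing ECG could not be identified. ECG, hospitalization and inpatient dosing data are all listed (SAP 3.6.5, 3.6.1, 3.3.7).
- That the bias in RASP from a late draw can be calculated from the reported drug half-lives. Drug level is not an endpoint, and the documents give no relation between the two.

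**Conclusion.** The Day 1 conflict stands on the visible text. Three timed PD and ECG measurements are required of outpatients whose dose the same section sends home. If the text is followed, those values will be missing or mistimed for every subject who starts as an outpatient. The 4 later vital-sign sets are ambiguous rather than clearly in conflict. The Day 7 ECG is a wording inconsistency with a likely intended answer, inpatients only. The PD timing on Days 7 to 28 needs clarification.

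The severity is minor to moderate. The trial is exploratory and not formally powered. The outpatient share is unknown, so no trial-level loss can be stated. The conclusion assumes that Appendix A and the redacted parts of 5.5.2 and 5.5.3 do not already resolve the matter, and confidence is medium for that reason.

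**What to change.** Subject to what Appendix A and Sections 5.5.2 and 5.5.3 already say:

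1. In Protocol 6.3 and 6.3.1, remove Day 1 from the home-dosing text. Give the first outpatient dose at the Day 1 visit, with at least the post-dose PD sample and the 1-hour ECG. State that the 6-hour ECG and the 2 to 8 hour vital signs are for inpatients only, unless the sponsor intends otherwise.
2. On Days 7, 13, 22 and 28, have outpatients time the dose to the PD draw and record the clock time of that dose. In SAP 3.5, label a sample post-dose only if it was taken within 1 hour after a recorded dose.
3. In Protocol 8.10 and SAP 3.6.5, restrict the Day 7 ECG to inpatients, to match 6.3.3. Extending it to outpatients, who are on site that day, is the sponsor's choice.

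The cost is an outpatient Day 1 visit about 1 hour longer, one dose-time field and a few lines of text. Some PD samples may lose the post-dose label.
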